We will use a combination of subjective and objective measurements of sleep quality and efficiency to measure the impact of any sleep perturbations. The following objective metrics will be derived from visual/manual polysomnography (gold standard) & automated algorithm sleep staging:

1. Total sleep time.
2. Number of sleep cycles (switches of non-rapid eye movement (NREM) and rapid eye movement (REM) sleep).
3. Initial sleep and REM latencies (Time from beginning of study to the first stage of sleep, and from beginning of sleep to first REM sleep onset).
4. Duration of N1, N2, N3, and REM stages, and the duration of NREM (sum of N1,N2,N3)stages.
5. Sleep efficiency (100*total sleep time/time in bed).
6. Number of awakenings during night, including arousals per hour and duration of time spent awake after initial sleep onset (i.e., wake after sleep onset time)
7. Apnea-hypopnea and respiratory disturbance indices (the frequency of stop or reduced breathing episodes, and respiratory arousals per hour)
8. Periodic limb movement indices (the frequency of periodic leg movements of sleep per hour)
9. Measures of arousal during sleep
 - a. behavioural macrostate observations such as eye opening or blinking that can be assessed in video recordings

- b. microarousal observations defined exclusively by cortical fast frequency shifts (ie, >14 Hz rhythms) lasting 3 seconds or longer, with or without added autonomic measures of tachycardia.
 - c. Spectral composition of the sleep stage specific EEG over the 0.25-32 Hz frequency range
 - d.
10. Salivary samples to characterize awakening levels of cortisol will be obtained in the morning (~6AM) at the end of each night.
- 11.
12. Questionnaires will be administered to patients as per the list below:
 - Upon enrollment/prior to their visit:
 - The following questionnaires or tasks will be administered to or completed by both the Epilepsy and Parkinson's disease Cohort at specified time points (see schedule of events)
1. Neurological Exam & Mini-Mental State Examination (MMSE).
2. Current medications and medication history. Medications will be kept stable
3. Mood assessment with Beck Inventory for Anxiety and Depression
4. Quality of life evaluation (QOLIE-31) questionnaire.
5. Patient sleep diary (bedtime, awakening time, arousals/sleep disturbances, perceived sleep quality).
6. Karolinska Sleepiness Scale (KSS) (Akerstedt and Gillberg, 1990).
7. Profile of Mood States Scale (POMS) (McNair, Lorr and Doppleman, 1971)

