9.6. Description of study intervention(s), comparators and study procedures (clinical)

9.6.1. Description of study intervention(s)

We will use both an open and a closed-loop approach to investigate sleep perturbations through stimulation deep brain targets. As previously mentioned, FDA approved clinician or patient programmers specific to the implanted device will be used at the open-loop stage, to explore the effect of available stimulation patterns when they are synchronized with different sleep stages. A physician/sleep technician team will be overseeing the delivery of stimuli during real-time sleep scoring on testing nights. See Appendix A. for example stimulation paradigms

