Upon awakening (at a time decided based on the sleep diary), a salivary sample will be obtained for morning cortisol. Participants will complete specific tasks at the time of awaking, and again at 30 minutes and 60 minutes post awaking.. These tasks will consist of the KSS, Mood, KDT, , , and PVT.

During the intervening day, the patients will be allowed to read, watch television, and socialize with caregivers, as well as complete tasks and questionnaires.

Testing/stimulation night:

We will use the programmers in an initial open-loop approach during the first visit, to see if a pattern can help optimize sleep stages and perturb sleep patterns. We will reconfigure each subject with polysomnography system and ensure it is still operating per requirements. The intent is to provide a consistent environment over both nights. We will again capture EEG (and if available, intracranial data). We will use real-time classification of sleep architecture to perturb the networks with variants of stimulation (see tables per target in Appendix A). For the initial sleep cycles, we will be using manual (open loop) interventions by the sleep monitor and the site clinician and scientist. In parallel, the laptop algorithm will be running a prototype closed-loop control to demonstrate the bridge to automated closed loop control. The output of the algorithm and stimulation commands will be logged and compared to the manual interventions.

Upon waking, a salivary sample will be obtained for measuring of early morning cortisol. The cognitive tasks will be performed as listed previously, to assess sleep inertia and other response variables. Subjective questionnaires will be administered post-cognitive screen. Cognitive tests will continue throughout the day to assess variation in the patient's performance.

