9.8. Visit-3 Second EMU visit

The second visit will also consist of two nights of sleep recordings. We will once again connect the participant to the equipment and capture standard behavior and electrophysiological nature of brain in different stages (AWAKE, N1, N2, N3, REM) as well as intracranial data where available. This will happen at the beginning of both nights and be compared to the baseline. This visit will be largely informed by the sleep characteristics and stimulation results of the first visit.

Adaptive night: We will use real-time classification of sleep architecture to perturb the networks with variants of stimulation. The perturbations will be automatically generated by the adaptive algorithm, which will be informed from the data gathered during the first visit.

Control night: open loop stimulation (or off) will be applied, guided again by data obtained during the first visit.

Upon waking, salivary cortisol samples will be obtained as before. The cognitive tasks will be performed again to assess sleep inertia and other response variables. Subjective questionnaires will be administered post-cognitive screen. Cognitive tests will continue for an additional post-wake to fully gauge impacts on sleep inertia. Testing and questionnaire schedule will be the same during both visits.

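### Before it generates stimulation itself, the closed-loop prototype is compared only with real-time staff interventions and never with the gold-standard sleep scoring

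*Combined protocol and SAP*

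**What the plan says.** Section 9.7 describes the testing night of the first EMU visit. On who controls stimulation: "For the initial sleep cycles, we will be using manual (open loop) interventions by the sleep monitor and the site clinician and scientist". On what runs beside them: "the laptop algorithm will be running a prototype closed-loop control to demonstrate the bridge to automated closed loop control". On how the two are related: "The output of the algorithm and stimulation commands will be logged and compared to the manual interventions". It gives no agreement measure, no threshold and no other reference.

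Section 9.6.1 shows what the manual interventions rest on: "A physician/sleep technician team will be overseeing the delivery of stimuli during real-time sleep scoring on testing nights".

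Section 7 says the objective sleep metrics are "derived from visual/manual polysomnography (gold standard) & automated algorithm sleep staging". The two sources stand side by side, and nothing says that one will be checked against the other.

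Section 9.8 then hands over control on the adaptive night: "The perturbations will be automatically generated by the adaptive algorithm, which will be informed from the data gathered during the first visit".

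Section 11.2 (statistical methods) contains no validation of the algorithm. The analyses between the visits in section 11.5 ask whether the assumptions on timing and desired effects held. They do not mention whether the algorithm stages sleep correctly.

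**The concern.** An adaptive night is informative only if stimulation falls in the stage it was meant for. Before that night, the one stated check on the algorithm uses human calls made in real time as its yardstick. Those calls have their own errors, and an algorithm that makes the same errors will look right. The manual interventions are also settings, not stages. Several stages can share a setting, so matching the setting need not mean recognising the stage.

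What is at stake is how the adaptive night is read. Section 6 lists the effect of stimulation on sleep stages among the primary objectives. If that night shows no effect and trigger accuracy by stage is unknown, two explanations cannot be told apart: closed-loop stimulation did nothing, or it was delivered in the wrong stage.

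**Working it through.** The documents give no accuracy, agreement or threshold figure for the algorithm, so there is no plan figure to reproduce. Two checks were made.

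**Check 1: what matching commands shows on the protocol's own examples.** Inputs are the two night-2 stimulation rows in Appendix A, sleep segments only. Counts are by segment because no durations are given.

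| | N1 | N2 | N3 | REM | N1 | N2 | REM |
|---|---|---|---|---|---|---|---|
| Example 1 | off | off | low | off | off | low | off |
| Example 2 | off | off | off | high | off | off | high |

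- In each example 5 of 7 segments are off. A rule that always outputs off, with no staging at all, matches 5/7 = 71% of the commands. It gets 0 of the 2 stimulated segments right.
- Two unrelated sequences with the same mix would match (5/7)² + (2/7)² = 25/49 + 4/49 = 29/49 = 59% of the time.
- In example 1, off covers N1, the first N2 and REM, while low covers N3 and the second N2. The same stage carries two settings and the same setting carries three stages.
- In example 2, off covers N1, N2 and N3. An algorithm unable to tell those three apart would still match all 7 commands if it recognised REM.

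**Check 2: what agreement on stage calls says about accuracy.** Let *a* be the accuracy of the real-time staff calls against the gold standard and *g* the agreement between algorithm and staff.

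- The algorithm is right at least whenever staff are right and the two agree. Lower bound: max(0, *a* + *g* − 1).
- It is wrong whenever staff are right and the two differ, or staff are wrong and the two agree. Upper bound: 1 − |*a* − *g*|.

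All values of *a* and *g* below are assumptions.

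| *a* | *g* | lowest algorithm accuracy | highest algorithm accuracy |
|---|---|---|---|
| 0.70 | 0.90 | 0.60 | 0.80 |
| 0.80 | 0.70 | 0.50 | 0.90 |
| 0.80 | 0.90 | 0.70 | 0.90 |
| 0.90 | 0.90 | 0.80 | 1.00 |
| 0.80 | 1.00 | 0.80 | 0.80 |

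The last row is the shared-error case: perfect agreement means the algorithm is exactly as accurate as staff, mistakes included.

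In the other direction, suppose both are 85% accurate. Agreement can then lie anywhere from 0.85 + 0.85 − 1 = 70% to 100%. With independent errors spread evenly over the four wrong stages it would be 0.85² + 0.15²/4 = 73%. The same accuracy therefore fits low or complete agreement.

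**The case against.** The strongest reply is that the protocol claims little for this comparison. It logs, compares and demonstrates. It has no pass mark, and no outcome in section 6 uses the result. The staff calls come from a physician and sleep technician team scoring the same polysomnography, so the comparator is human scoring done live and not something unrelated to the gold standard. Most of this stands, and it limits the point in four ways.

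- A reader might infer that the plan makes readiness for the adaptive night depend on agreement with staff. It does not; no such rule is written.
- A reader might infer that agreement says nothing about accuracy. The bounds above show otherwise. With staff 85% accurate, agreement of 90% puts the algorithm between 75% and 95%, and agreement of 30% caps it at 45%. The evidence is weak and indirect, not absent.
- A reader might infer that the algorithm would merely detect the staff's switching in the EEG. The documents give neither its inputs nor its artefact handling, so this is possible but not shown. EEG recorded under stimulation is no fault in itself, because the algorithm must read such EEG on the adaptive night.
- A reader might count agreement by 30-second epoch and conclude that an algorithm issuing no commands would score 98% to 99%. That needs a metric, a night length and a number of commands that the plan does not give. The 71% figure rests on the plan's own examples.

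What the reply does not answer is that no planned analysis asks whether the algorithm's stage calls were correct, although the polysomnography and the logs needed to ask it will be there.

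**Conclusion.** The point holds as a limited gap in the analysis. The only stated comparator for the prototype before it generates stimulation is the real-time manual intervention, and no comparison with the manual scoring that section 7 calls the gold standard is planned. On the Appendix A examples a rule with no staging matches 71% of commands by segment. On stage calls, 90% agreement with staff who are 80% accurate leaves algorithm accuracy anywhere from 70% to 90%. The first figure assumes that the examples are typical and weights segments equally. The second uses assumed accuracies.

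The documents do not support calling the comparison worthless or the adaptive night invalid. For a feasibility study this is a worthwhile improvement, not a defect that blocks the study.

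**What to change.** Change the analysis wording in section 9.7, with a matching line in 9.8:

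- Make manual scoring of the testing-night polysomnography the reference for both the algorithm's stage calls and the real-time staff calls. State that it is done without sight of the algorithm output and the command log.
- Report sensitivity, positive predictive value and delay from stage onset, by stage, for algorithm and staff side by side. Add the share of commands that fell in the intended stage.
- Use all epochs, and report those before and after the first change of setting separately. Restricting to EEG before a switch within each bout would not work. Such EEG still carries the previous setting (in example 1, REM begins under low). Some transitions involve no switch (N1 to N2 is off to off). It would also discard stimulated EEG of the kind the algorithm must read on the adaptive night.
- Keep agreement with the manual interventions as a description only.
- Repeat the check on the adaptive-night recording, so that a null result can be separated from mistimed stimulation.

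The recordings and logs are already planned, so no patient procedure is added. The cost is a little more scoring and analysis. Estimates by stage will be imprecise in each patient. In the Appendix A examples the first change comes at N1, so the group of epochs before it will contain little sleep.

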9.8. Visit-3 Second EMU visit

The second visit will also consist of two nights of sleep recordings. We will once again connect the participant to the equipment and capture standard behavior and electrophysiological nature of brain in different stages (AWAKE, N1, N2, N3, REM) as well as intracranial data where available. This will happen at the beginning of both nights and be compared to the baseline. This visit will be largely informed by the sleep characteristics and stimulation results of the first visit.

Adaptive night: We will use real-time classification of sleep architecture to perturb the networks with variants of stimulation. The perturbations will be automatically generated by the adaptive algorithm, which will be informed from the data gathered during the first visit.

Control night: open loop stimulation (or off) will be applied, guided again by data obtained during the first visit.

Upon waking, salivary cortisol samples will be obtained as before. The cognitive tasks will be performed again to assess sleep inertia and other response variables. Subjective questionnaires will be administered post-cognitive screen. Cognitive tests will continue for an additional post-wake to fully gauge impacts on sleep inertia. Testing and questionnaire schedule will be the same during both visits.

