9.5. Blinding and code-breaking

There will be no blinding in the study and therefore no code-breaking procedure is required.

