11.3. Sample Size Determination

This is a feasibility study into recruiting and conducting the study procedures in patient populations. Given the exploratory and novel nature of this study, effect sizes are as of now, unknown. We are collecting from different groups bearing in mind that a minimum n=3 is required for the most rudimentary statistics based on patient number. We therefore expect 15 patients to be the lowest bound for 5 different DBS electrode locations. There will be multiple comparable stimulation epochs per patient, across three nights (second night of first visit and both nights of second visit). The number of sleep stages and cycles per night will vary between participants, with an added unknown being the effect of the disease state on sleep. However, this within- and across-subject comparison will boost statistical power. Further support that an N-of-1 trial design can be used for closed-loop DBS research and provide individualized, precision data to inform device development, was published recently (Stevens and Gilbert 2020).

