11.5. Decision points

As specified in section 9.7., interim analyses of each patient's baseline data will be performed after the first night of the first visit. This will help establish a familiarity with each participant's sleep stage duration and EEG morphology, their maximum sleep depth as well as the presence of pathological sleep features. Based on this knowledge, decisions on the timing of the stimulation during the second night will be made by the PI and sleep scientist team, as well as basic assumptions on the desired effects. Following the first visit, further interim analyses will determine to what degree these assumptions were correct, so that stimulation patterns can be explored further during the second visit.

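### Section 9.8 sets no order for the adaptive and control nights, so a common order would leave the closed-loop contrast inseparable from a night-within-visit effect

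*Combined protocol and SAP*

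**What the plan says.** Section 9.8 provides that "The second visit will also consist of two nights of sleep recordings". It then describes them under two labels. For the adaptive night: "The perturbations will be automatically generated by the adaptive algorithm, which will be informed from the data gathered during the first visit". For the other: "Control night: open loop stimulation (or off) will be applied, guided again by data obtained during the first visit". The adaptive night is described first, but the section does not say which night comes first.

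Section 11.5 places the decision point that feeds this visit after the first visit ("Following the first visit, further interim analyses will determine to what degree these assumptions were correct") and mentions none between the two later nights. Section 9.5 states: "There will be no blinding in the study and therefore no code-breaking procedure is required". Section 11.3 counts both nights towards the within-patient evidence: "There will be multiple comparable stimulation epochs per patient, across three nights (second night of first visit and both nights of second visit").

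Section 11.2 leaves the choice of test open and names no night, period or order term. Section 11.7 gives no numerical significance level. Neither section 9 nor section 11 randomises, counterbalances or alternates the nights. Only the heading of Appendix B, the schedule of procedures, was available for this review.

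**The concern.** The second visit holds the study's only same-visit comparison between closed-loop stimulation actually delivered to the patient and open-loop or no stimulation. Within that visit the delivery mode is constant over a night, so epochs within one night cannot supply the comparison.

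Two consecutive nights in a monitoring unit may differ for reasons unrelated to stimulation, such as readjustment to the unit, accumulated sleep loss, or further repetition of the test battery. If all patients take the nights in the same order, any such difference falls on one side of the contrast. If staff who know the conditions choose the order patient by patient, the confounding depends on how unbalanced the choices turn out to be.

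The first visit is different. Section 9.7 needs the baseline night first because it generates the patient-specific perturbations. Section 9.8 states no such dependence between the adaptive and control nights, so their order appears free to be randomised.

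**Working it through.** **Inputs from the protocol.** There are two nights at the second visit (9.8). Section 11.3 says "a minimum n=3 is required for the most rudimentary statistics based on patient number" and takes five electrode locations, so the lower bound is 3 × 5 = 15, which reproduces the stated figure. The protocol gives no effect size, SD, night effect, numerical alpha or named test for this contrast.

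**Assumptions for illustration.** Paired t-test, two-sided alpha 0.05, one outcome, SD of the paired difference set to 1, independent patients, no true closed-loop effect.

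**Model.** For each patient let d = adaptive minus control, τ = closed-loop effect, π = second-night minus first-night effect, and s = +1 if the adaptive night is second, −1 if first. Then E(d) = τ + sπ.

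**Step 1: common order.** With s the same for all, the design columns [1, s] have rank 1. The data estimate τ + π or τ − π, and no sample size separates the two terms. The bias equals π in size.

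**Step 2: false-positive rate under a common order, n = 15.** The t statistic is noncentral with 14 degrees of freedom and noncentrality π√15; the critical value is 2.145.

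| Assumed π (SD of d) | π√15 | Rejection rate with τ = 0 |
|---|---|---|
| 0.3 | 1.16 | 19% |
| 0.5 | 1.94 | 44% |
| 0.8 | 3.10 | 82% |

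More patients make this worse: at n = 30, π = 0.5 gives about 75%.

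**Step 3: balanced order with an order term.** With 8 patients in one order and 7 in the other, the design has rank 2. The estimate is the average of the two order-group means, in which +π and −π cancel. In 200,000 simulated trials the rejection rate was 5% at every π from 0 to 1 SD.

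**Step 4: precision.** SE = √[(1/a + 1/b)/4] for split a/b, against 1/√15 = 0.2582 under a common order.

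| Split | SE (SD of d) | Increase |
|---|---|---|
| 8/7 | 0.2588 | 0.2% |
| 9/6 | 0.2635 | 2.1% |
| 10/5 | 0.2739 | 6.1% |

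**Step 5: where to balance.** Blocks of two inside each target of three leave one unpaired patient per target, five in all. The split is then 8/7 with probability 20/32, 9/6 with 10/32 and 10/5 with 2/32. Within a single target of three the best split is 2:1, where an unadjusted mean keeps a bias of π/3. Simple randomisation gives all three the same order with probability 2 × 0.5³ = 0.25. Balance should therefore be set across the whole sample.

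**Step 6: carry-over.** Suppose the adaptive night carries over by L into a following control night and the control night carries nothing over. The two orders have means τ − π − L and τ + π, and their average is τ − L/2. Balancing removes π but leaves −L/2.

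**The case against.** The strongest reply is that this is an unblinded feasibility study in which adaptive versus control is not a named outcome. Section 9.6.2 lists usual settings, on versus off, and patterns against one another. That is true: the contrast is inferred from the label given to the control night and from the general within-patient comparisons. However, section 6 makes the effect on sleep stages a primary objective and section 11.2 intends to look for statistical significance, so the comparison is likely to be made.

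Four stronger readings are tempting, and the documents do not support them.

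- A reader might infer that the adaptive night is fixed first. Section 9.8 only describes it first, and Appendix B might state an order.
- A reader might call the pair the only direct test of the closed-loop approach. Section 9.7 also has the algorithm's output logged and compared with the manual interventions at the first visit. That tests the algorithm's commands, not their effect on sleep, so the accurate claim is the narrower one about delivered stimulation within one visit.
- A reader might infer that the second visit depends on first-visit data alone. Section 9.8 says this is largely so, and section 11.2 mentions updating a hidden Markov model without saying when. Free order is a fair inference, not a stated fact.
- A reader might treat practice on the tests as uncontrolled. Section 9.7 runs the battery on the baseline day to reduce novelty, and it is repeated before the second visit. Some practice effect may remain, but it is partly handled.

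Section 9.8 also plans a standard recording on each of these nights: "This will happen at the beginning of both nights and be compared to the baseline". This offers a partial reference, but no stated analysis uses it to adjust the contrast. It cannot correct whole-night or next-morning outcomes such as sleep efficiency, awakenings, cortisol or vigilance.

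**Conclusion.** The point holds as a gap in the design. With no stated order, no randomisation and no order term, the plan allows a common order, and a common order makes the closed-loop effect inseparable from a night effect. That structural conclusion needs no assumed effect size.

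The 19%, 44% and 82% figures are illustrations. They rest on an assumed common order, night effect, test and alpha, and on treating 15 patients as one homogeneous set of pairs even though the control condition may be open loop or off. They do not estimate the error rate this study will have.

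Nor should a reader infer that randomising the order makes the contrast free of bias. It removes an additive night effect; a one-sided carry-over L still leaves −L/2. If Appendix B already specifies a randomised or balanced order, the remaining gap is the missing order term in the analysis.

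**What to change.** In section 9.8, state that the order of the adaptive and control nights is randomised 1:1 and balanced across the whole sample, for example with blocks that run on across targets, so that 15 patients split about 8/7. Make Appendix B agree.

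In section 11.2, state that the within-patient adaptive-minus-control difference is analysed with a term for order, and that carry-over from one night to the next cannot be excluded and is reported as a limitation.

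This is a cheap improvement. It needs a randomisation list, a few sentences and one degree of freedom (14 to 13 at n = 15). The standard error rises by about 0.2% at 8/7, or about 6% if the split came out 10/5. No night, patient or change in the stimulation delivered is added.
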